4.4.2.2 Comparison of TTR of All Symptoms to Historical Control

It is unethical to treat IC patients with placebo. Nevertheless, it is important to ascertain whether treating IC patients for influenza is still better than not treating them. Given the ethical constraint, the next best possible comparison available is against historical placebo controls. Thus, any difference between these two groups will be due to both IC status (yes/no) and oseltamivir effect. It will not be possible to differentiate both effects statistically. Historical controls will come first and foremost from pivotal historical oseltamivir studies where otherwise healthy (OwH) were enrolled. The main comparison of active treatment with historical control placebo will be based on a 1:1 matching of all adult NV20234 patients with OwH placebo patients from the pivotal studies. All patients in the adult mITTi population will be matched to historical patients (from the pivotal studies) that received a placebo.

There are three types of matches in order of priority:

1. Patients will be matched 1:1 within viral strain and then by age with ± 5 years caliper (the lowest limit being 18) and gender. Any remaining unmatched individual will be matched by age and gender alone. Only

pivotal studies will be used. Outputs in [appendix 5](#) refer to this matching rule.

2. Patients will be strictly matched 1:1 by age as above, gender and influenza strain. Only pivotal studies will be used. There will probably leave more unmatched patients but those matched will be more similar than in 1.
3. Patients will be matched 1:>1 as in 1 above using pivotal and non-pivotal but relevant historical studies. Additional matching by time between symptoms onset and first treatment (possibly with a caliper) will be used if closer matching is required. This is a sensitivity analysis captured in section [4.4.4](#).

In cases where those matching rules are not sufficient, i.e. more than one patient in the 1:1 placebo matching, an additional rule will be the elapsed time from first symptoms to first dose. If several matches are still available in the 1:1 ratio, one match will be chosen at random (the seed of the random number generator will be kept for reproducibility).

Any patient from study NV20234 who has not been matched will not be included in these analyses. Matches will be done independently for historical placebo and historical treated. Modifications of the matching rules above may be permitted if scientifically required, e.g. matching by time in 3 above requires a window. The ITTi population in historical studies is equivalent to the current mITTi population.

The pivotal studies to be used are: WV15671 (18-65y, OwH, USA, placebo-conventional-double) and WV15670 (18-65y, OwH, Europe, Canada, Hong-Kong, placebo-conventional-double). Potential additional studies include: WV15730 (18-65y, OwH), M76001 (13-80y, OwH, placebo-conventional) and WV15758 (1-12y, OwH, placebo-conventional).

A similar comparison may be done between current IC patients and historical patients defined as at risk. There may be a 1:1 and 1:>1 matching ratios. The historical studies with patients at risk include WV15812 (≥ 13 y, placebo-conventional) and WV15872 (≥ 12 y, placebo-conventional). Additional studies in elderly (>65 years of age) are: WV15819, WV15876, WV15978 and WV15707 (see [Appendix 4](#)).

The following median differences in TTR of all symptoms (90% and 95% CIs) will be reported:

1. Comparison of conventional dose with matched placebo.
2. Comparison of double dose with matched placebo.
3. Comparison of combined conventional and double dose with combined matched historical placebo (if the results of the NV20234 dose group comparisons suggest responses are similar).

To aid interpretation of the results, the median TTR of all symptoms and associated 90% CIs will be plotted against historical placebo responses for a) NV20234 conventional dose b) NV20234 double dose c) NV20234 combined dose groups.

In addition to the comparison of NV20234 active with placebo patients from the pivotal studies, a *treatment* historical control dataset will be created from the same adult treatment studies, matching NV20234 patients randomized to the conventional dosing arm with the conventional dose from the adult treatment studies. This will enable an informal comparison of the treatment response of IC patients with the treatment response in otherwise healthy patients. Patients will be matched using the same rules as those for historical control.

The full specifications for historical control groups can be found in [Appendix 4](#). The final set of historical placebo patients will be confirmed prior to treatment unblinding and database lock.

4.4.2.3 Continuous Endpoints

Continuous endpoints will be summarized by treatment group using descriptive statistics N, mean (geometric mean where appropriate), SD, median, and range.

This will apply to: duration of hospitalisation; absolute and change from baseline over time in \log_{10} viral load from quantitative RT-PCR (vp/mL), \log_{10} viral load titer from culture (\log_{10} TCID₅₀/mL), AUC viral load titer, peak viral load titer, AUE total symptom score, and AUE individual symptom scores.

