2.2.2.2 Viral load

Viral load is the number of viral particles per mL of blood. It is reported in \log_{10} scale and expressed in 1) virus particles/mL (\log_{10} vp/mL) calculated from the quantitative RT-PCR assay (reverse transcriptase polymerase chain reaction) and 2) 50% tissue culture infectious dose (\log_{10} TCID₅₀) obtained after viral culture.

- Viral load change from baseline over time expressed in \log_{10} vp/mL, where baseline is defined as the pre-dose day 1 result.
- Viral load change from baseline over time expressed in \log_{10} TCID₅₀/mL, where baseline is defined as pre-dose day 1 result. \log_{10} TCID₅₀/mL is calculated as: $TCID_{50} = -\left(X_0 - d/2 + d \sum_{x=p=1}^{x_{min}} p_x\right)$, (Ramakrishnan MA, 2016) where:

X_0 = positive logarithm of the highest dilution at which all quadruplicate wells are positive in the haemagglutination assay or NP-ELISA,

$p_x = \frac{r_x}{4}$, where r_x is the number of positive wells (out of 4) at dilution x ,

$x_{p=1}$ is maximum dilution at which all 4 wells are positive,

x_{min} is the dilution at which all four wells are negative for the first time, and

d is the \log_{10} dilution factor, i.e. $\log_{10}10^{-1} = -1$.

N.B. The data contains two variables: X_0 and X_1 , where $X_1 = -\sum_{x=p=1}^{x_{min}} p_x$ and $X_0 = -X_0$ (see above). Thus, programmatically,

$$TCID_{50} = X_0 - 0.5 + 0.25X_1$$

- Area under the viral titer curve calculated applying the trapezoidal rule to the \log_{10} TCID₅₀/mL viral load titer.
- Area under the viral titer curve calculated applying the trapezoidal rule to the \log_{10} vp/mL viral load titer.
- Peak viral titer per arm defined as the maximum \log_{10} TCID₅₀/mL.
- Peak viral titer per arm defined as the maximum \log_{10} vp/mL.

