4.4 EFFICACY ANALYSIS

All efficacy endpoints are considered secondary or exploratory. As no formal efficacy hypothesis is being tested, treatment differences presented in any efficacy analyses will be reported with associated confidence intervals (CIs) only. Efficacy endpoints will be summarized by age group. All summaries and analyses are described below and listed in [Appendix 5](#). All efficacy analyses will be based on the mITTi and ITTi populations. ITT will be presented for the main efficacy TTR summary tables (all symptoms and temperature only) to investigate the effect of treatment in a “real world” scenario, i.e. unknown infection status and/or adherence. N.B. Regulatory bodies have asked for these outputs in pivotal studies.

All efficacy summaries and analyses will be carried out separately for adults (patients ≥ 18 years) and paediatrics (patients <13 years old). Adolescent data (patients aged between ≥ 13 and <18 years old) will be listed as appropriate.

As the symptom data are recorded on patient diaries, data errors cannot be queried. Obvious data errors, i.e. temperature 100°C , will be excluded and documented. For duplicated data, the worst evaluation will be used to obtain conservative estimates.

The endpoints as described in the protocol have been expanded to give sufficient information of the derivations required, e.g. *symptom scores* was the endpoint defined in the protocol but *Time To Resolution of symptom scores* is how it is described in the SAP.

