6. APPENDIX 1: PROTOCOL SYNOPSIS

TITLE: A DOUBLE BLIND, RANDOMIZED, STRATIFIED, MULTI-CENTER TRIAL EVALUATING CONVENTIONAL AND DOUBLE DOSE OSELTAMIVIR IN THE TREATMENT OF IMMUNOCOMPROMISED PATIENTS WITH INFLUENZA

PROTOCOL NUMBER: NV20234

VERSION NUMBER: F

EUDRACT NUMBER: 2006-002468-24

IND NUMBER: 53,093

TEST PRODUCT: oseltamivir (Tamiflu® RO 64-0796)

PHASE: IIIb

INDICATION: Treatment of influenza in immunocompromised patients

SPONSOR: F. Hoffmann-La Roche Ltd

Objectives

Primary

To evaluate prospectively the safety and tolerability of oseltamivir for the treatment of influenza in IC patients under standard and double dose, and characterize the effects of oseltamivir in IC patients on the development of resistant influenza virus (see 4.6).

Secondary

To evaluate the effects of conventional and double dose oseltamivir in IC patients on:

- The population pharmacokinetics of *both oseltamivir and oseltamivir carboxylate* in IC patients with confirmed influenza infection, through the application of established population pharmacokinetic (PK) models to the sparse plasma concentration data generated.
- The virologic course of influenza (proportion shedding and viral loads at different timepoints)
- The time to resolution of influenza symptoms
- The clinical course of influenza (fever, symptoms, secondary illnesses as evidenced by otitis media, bronchitis, pneumonia, or sinusitis)
- To explore the relationship of metrics of exposure (e.g., AUC, C_{min}) to relevant pharmacodynamic endpoints

Study Design

Description of Study

This is a double-blind, randomized, multi-center trial of twice daily, conventional and double dose oseltamivir for the treatment of influenza in IC patients. Patients will be stratified by age (<13 vs. >12 years), transplant status (yes vs. no), time since onset of flu symptoms and treatment start (up to 96 hours) (≤ 48 vs. >48 hours) and vaccination status (yes vs. no).

Number of Patients

A minimum of 166 (83 per arm) to allow an adequate number of influenza A patients per arm; including 50 transplant recipients *and at least 15 paediatric patients*.

Number of Centers

Approximately 125 centers in the Northern and Southern Hemispheres

Target Population

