For the primary objective of evaluating the safety of oseltamivir conventional and double dose treatments, AEs, physical examinations, tissue rejection and/or graft versus host disease in transplant patients, laboratory tests, and vital signs will be summarized and compared with the known safety profile of the drug. For the summary of the development of resistance for each treatment arm, 95% confidence intervals will be provided with the estimated rates.

For the secondary objective of evaluating the efficacy of oseltamivir as measured by the time to resolution of influenza symptoms, the following two assessments will be made independently of each other and without regard to the outcomes in each case.

- Comparison to placebo control from pivotal registration trials

From the integrated efficacy database associated with the oseltamivir treatment approval, a population of placebo treated patients will be established that is comparable to patients in the current study whose first dose of study drug was within 48 hours of symptom onset. For this population, a median time to resolution of all clinical influenza symptoms will be determined along with its 95% confidence interval.

- Assessment of relative efficacy

The two dose groups will be compared to each other by estimating the difference in the median times to alleviation of symptoms and deriving an associated 95% confidence interval.

The following are the model-derived PK secondary endpoints for *oseltamivir and oseltamivir carboxylate*: steady-state AUC, C_{max} , and C_{trough} .

7. **APPENDIX 2: SCHEDULE OF ASSESSMENTS**

Table A2.1. Schedule of Assessments and Procedures

	Baseline	Treatment					Follow-up		
Study Day	1 (pre-dose)	1	2 or 3 ^{f,g}	6 ^{f,g}	8 ^{f,g}	11 ^{g,h,i}	15 ^g	40 ^{g,j}	
Informed Consent/Assent ^l	x								
Medical history	x								
Demographics	x								
Height and weight	x					x			
Pregnancy Test ^a	x					x		x	
Rapid diagnostic test for influenza virus shedding						x			
RIDTPCR/Culture for confirmation of influenza virus	x								
Safety Labs ^b	x					x			
Physical Examination	x					x		x	
Vital Signs (including pulse, respiratory rate, temperature, blood pressure)	x		x	x	x	x	x	x	
Nasal and throat swabs for viral shedding and viral load ^{c,d}	x		x	x	x	x	x	x	
PK sampling (blood) ^l						x ^m			
Review of patient diary data ^e			x	x	x	x	x	x	
Drug Administration		←—————→							
Collection of unused study drug and empty containers						x			
Previous Diseases	x								

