TTR fever	Kaplan-Meier	Treatment median [90% CI] Responses for : NV20234 conventional, NV20234 double, NV20234 pooled, historical treatment conventional, historical treatment double, historical placebo for conventional, historical placebo for double, historical placebo for pooled.	mITTi	Benchmarking plot**	1) Overall 2) Age cohort (>= 18 Y, < 18 Y) All CI's on one plot but also split by a) pooled b) conventional c) double	g_km_t1_t2_hist plac_treat_RES F_MITI_AD_90 g_km_t1&2_hist plac_treat_RES F_MITI_AD_90 Repeated 1:1 and 1:>1 matches
AUC total symptom scores	Median, IQR	Treatment Responses by treatment arms	mITTi, ITT, ITTi	Dose-Response main summary for this endpoint	Adults only	g_auc_ALLEVA S_AD t_auc_ALLEVAS AD
AUC total symptom scores	Median, IQR	Treatment median [IQR] for: NV20234 conventional, NV20234 double, NV20234 pooled, historical treatment conventional, historical treatment double, historical placebo for conventional, historical placebo for double, historical placebo for pooled.	mITTi	Benchmarking plot	For adults only : All plots on one plot but also split by a) pooled b) conventional dose c) double dose	g_km_t1_t2_hist plac_treat_AUC ALLEVAS_MITI_ AD_90 g_km_t1&2_hist plac_treat_ALLE VAS_MITI_AD_ 90 Repeated 1:1 and 1:>1 matches
AUC individual symptom score	Median, IQR	Treatment Responses by treatment arm	mITTi	Dose-Response main summary for this endpoint	Adults	g_auc_ALLEVIS _AD t_auc_ALLEVIS _AD
AUC viral titer	Median, IQR	Treatment Responses by treatment arm	mITTi	Dose-Response main summary for this endpoint	Adults Children	g_ef_auc_AUCC LT_MITI_AD t_ef_auc_AUCC LT_MITI_AD

						t_ef_auc_AUCC LT_MITI_CH t_ef_auc_AUCP CR_MITI_CH t_ef_auc_AUCP CR_MITI_CH
AUC viral titer	Plot Median, IQR	Treatment median [IQR] Responses for: NV20234 conventional, NV20234 double, NV20234 pooled, historical treatment conventional, historical treatment double, historical placebo for conventional, historical placebo for double, historical placebo for pooled.	mITTi	Benchmarking plot	All plots on one plot but also split by a) pooled b) conventional c) double	g_km_t1_t2_hist plac_treat_AUC CLT_MITI_AD_90 g_km_t1&2_hist plac_treat_AUCCLT _MITI_AD_90 Repeated 1:1 and 1:>1 matches
Peak viral titer	Median, IQR	Treatment Responses by treatment arms	mITTi, ITT, ITTi	Dose-Response main summary for this endpoint	a) Adults b) Children	t_ef_auc_PEAK CLT_MITI_AD t_ef_auc_PEAK CLT_MITI_PE t_ef_auc_PEAK PCR_MITI_AD t_ef_auc_PEAK PCR_MITI_PE

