Virus shedding	Proportions	Percentage of patients with viral shedding by baseline and planned visit.	mITTi	Main summary table	a) Adults b) children	t_ef_shed_CLTR _MITI_AD t_ef_shed_CLTR _MITI_CH t_ef_shed_PCR _MITI_AD t_ef_shed_PCR MITI_CH

Viral Load RT-PCR	Change from baseline in viral load RT-PCR	Summary Statistics (Mean, SD, Median, Range)	mITTi	Main summary table	Adults Children	t_ef_cfb_PCR_MITI_AD t_ef_cfb_PCR_MITI_CH
Viral Load Culture	Change from baseline in viral load from culture	Summary Statistics (Mean, SD, Median, Range)	mITTi	Main summary table	Adults Children	t_ef_cfb_CLTR_MITI_AD t_ef_cfb_CLTR_MITI_CH
Secondary Illnesses (SI)	summary only	N(%) by treatment group	Safety	Main summary table	1) Overall 2) Adult 3) Children Split by : a) any SI starting at any time b) any SI starting at any time that is treated with ant biotics c) SI started >=48 hours after start of study treatment that is treated with ant biotics	t_ae_secil_MITI t_ae_secil_ANTI B_SE

11. **APPENDIX 6: VIRAL MUTATIONS ASSOCIATED WITH RESISTANCE**

Table A6.1. USPI table with Neuraminidase (NA) Amino Acid Substitutions Associated with Reduced Susceptibility to Oseltamivir*

Influenza A N1 (N1 numbering in brackets)	
I117V (I117V)	E119V (E119V)
R152K (R152K)	Y155H (Y155H)
F173V (F174V)	D198G/N (D199G/N)
I222K/R/T/V (I223K/R/T/V)	S246N (S247N)
G248R+I266V (G249R+I267V)	H274Y (H275Y)
N294S (N295S)	Q312R+I427T (Q313R+I427T)
N325K (N325K)	R371K (R368K)
Influenza A N2	
E41G	
E119I/V	D151V
I222L/V	Q226H
SASG245-248	S247P
R292K	N294S
Influenza B (B numbering in brackets)	
E119A (E117A)	
P141S (P139S)	G142R (G140R)
R152K (R150K)	D198E/N/Y (D197E/N/Y)
I222L/T/V (I221L/T/V)	A246D/S/T (A245D/S/T)
H274Y (H273Y)	N294S (N294S)
R371K (R374K)	G402S (G407S)

*All numbering is N2, except where indicated

Haemagglutinin (HA) Amino Acid Substitutions Associated with Reduced Susceptibility to Oseltamivir

According to the current Tamiflu label, HA mutations should include A28T and R124M in influenza A H3N2 and H154Q in H1N9.

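### The SAP plans no dose difference with a confidence interval, and no adjustment by regression for pre-dose titre, for viral load or viral AUC

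*SAP*

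**What the plan says.** The synopsis in SAP Appendix 1 lists, among the secondary objectives for the two doses, "The virologic course of influenza (proportion shedding and viral loads at different timepoints".

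The method is in section 4.4.2.3: "Continuous endpoints will be summarized by treatment group using descriptive statistics N, mean (geometric mean where appropriate), SD, median, and range". The endpoints it covers include "absolute and change from baseline over time in" log10 viral load by RT-PCR and by culture, as well as AUC and peak titre. Section 2.2.2.2 defines the change "where baseline is defined as the pre-dose day 1 result".

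Section 4.8 and Appendix 5 list the outputs. The RT-PCR row of Appendix 5 reads "Change from baseline in viral load RT-PCR", with mean, SD, median and range; the culture row is the same. AUC and peak titre have median and IQR by arm, and their purpose is given as "Dose-Response main summary for this endpoint".

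Section 4.4 sets the stance for efficacy: "treatment differences presented in any efficacy analyses will be reported with associated confidence intervals (CIs) only". The schedule in Appendix 2 has "Nasal and throat swabs for viral shedding and viral load" before the first dose and at every later visit.

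**The concern.** The SAP gives other endpoints a between-arm estimate. Section 4.4.2.1 plans Hodges-Lehmann differences with CIs for the time-to-event endpoints, and section 4.4.2.4 plans a probability difference with CI for antibiotic use. Viral load and viral AUC get neither, although the dose effect on viral load is a stated objective. The reader must compare two columns by eye.

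That comparison is exposed to chance. Randomisation is stratified on transplant, time from symptom onset, vaccination and age (section 3.1), not on influenza type or pre-dose titre. If one arm starts with higher titres, the absolute values at follow-up tend to disfavour it and the change scores tend to favour it. The SAP does not say which display governs. AUC has no correction for the starting titre. Peak titre, as defined in section 2.2.2.2, does not exclude the pre-dose sample and so may simply be the baseline value.

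**Working it through.** **The plan's own figures.** The SAP states no power, SD or baseline to follow-up correlation for viral load, so there is no figure on this endpoint to reproduce. The 66% power in section 2.3 concerns time to resolution of symptoms (34 h, SD 98 h, two-sided 10% alpha, 75 per group). It reproduces as 66.7% with a two-sample rank-sum efficiency of 3/pi, and has no bearing here.

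**Inputs.**
- n = 75 evaluable per arm (section 2.3; 83 x 0.9 = 74.7), allocated 1:1 (section 3.1).
- Correlation rho between pre-dose and follow-up log10 titre: assumed, 0.3 to 0.7.
- Equal SD at baseline and follow-up and a linear relation: assumed. Results are in SD units.

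**Precision.** The variance of the arm difference is 2v/n, and the 95% half-width is 1.96 x sqrt(2v/75), where
- absolute value: v = 1
- change from baseline: v = 2(1 - rho)
- ANCOVA: v = 1 - rho^2

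| rho | v: absolute / change / ANCOVA | Half-width: absolute / change / ANCOVA | Variance saved vs absolute (rho^2) | Variance saved vs change, (1 - rho)/2 |
|---|---|---|---|---|
| 0.3 | 1 / 1.40 / 0.91 | 0.320 / 0.379 / 0.305 | 9% | 35% |
| 0.5 | 1 / 1.00 / 0.75 | 0.320 / 0.320 / 0.277 | 25% | 25% |
| 0.7 | 1 / 0.60 / 0.51 | 0.320 / 0.248 / 0.229 | 49% | 15% |

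Against the better of the two planned displays, the saving is 9%, 25% and 15%. The interval would be 5%, 13% and 8% narrower (0.305/0.320, 0.277/0.320, 0.229/0.248).

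**Chance imbalance.** The standard error of the baseline difference is sqrt(2/75) = 0.163 SD, with a 95% range of +/-0.32 SD. Suppose the double-dose arm starts 1 SE higher. With no dose effect, the expected double-minus-conventional difference is
- absolute values: rho x 0.163 = +0.049, +0.082, +0.114 SD at rho 0.3, 0.5, 0.7
- change scores: -(1 - rho) x 0.163 = -0.114, -0.082, -0.049 SD

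At each rho the two displays differ by the full 0.163 SD (for example 0.049 + 0.114). ANCOVA removes the shift in expectation.

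**Age split.** Section 4.4 analyses adults and paediatric patients separately, so no planned viral-load table has 75 per arm. The synopsis asks for at least 15 paediatric patients in total. At about 7.5 per arm the standard error of imbalance is sqrt(2/7.5) = 0.52 SD.

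**The case against.** The best defence is that the plan is openly descriptive. The co-primary endpoints are safety and resistance, all efficacy is secondary or exploratory, and section 4.9 says that no formal analyses will be carried out. The virologic comparison is not left wholly without an estimate either: time to cessation of viral shedding has Kaplan-Meier medians and Hodges-Lehmann differences with CIs, and shedding is presented by treatment group, age cohort and influenza type. Imbalance would also be partly visible, because section 4.3 tabulates influenza type and subtype by arm and the absolute viral loads include baseline.

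Much of this stands, and it rules out several stronger readings that a reader might infer:

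- *That the pre-dose titre is ignored.* It is not. Viral load is also summarised as change from it. What is missing is regression adjustment.
- *That the SAP contradicts section 4.4.* That sentence applies to differences that are presented, and none is planned for viral load.
- *That a planned estimate wastes precision.* There is no planned between-arm estimate to lose any.
- *That adjustment saves 25-35% of variance.* That holds only against change scores at a correlation of 0.3 to 0.5. The absolute values are also planned.
- *That pre-dose titre is the strongest predictor, or is available for everyone.* The documents say nothing on the first. On the second they show only that a swab is scheduled, not that each gives a usable quantitative result.

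Two parts of the defence do not answer the point. A difference with a CI and no test is estimation, which section 4.4 allows and the SAP uses elsewhere. And seeing an imbalance is not the same as allowing for it.

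**Conclusion.** The point holds as a missed improvement, not as an error. For viral load, viral AUC and peak titre the SAP plans per-arm summaries only, so the secondary objective on viral loads gets no estimated dose difference. The two viral-load displays respond to chance baseline imbalance in opposite directions, and AUC is uncorrected.

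The size rests on assumptions, because the documents give no SD or correlation. For rho from 0.3 to 0.7, ANCOVA would save 35% down to 15% of variance against change scores and 9% up to 49% against absolute values. Equal variances become doubtful once many patients are virus-negative. I have no corresponding figure for AUC. With the age split the arms are smaller than 75, which makes chance imbalance larger in each table. No primary conclusion is affected.

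**What to change.** Before unblinding, amend section 4.4.2.3 and Appendix 5 as follows, with a matching clause in section 4.9:

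1. Keep all per-arm summaries.
2. Add the double-minus-conventional difference with 95% CI, without a hypothesis test, for log10 vp/mL and log10 TCID50/mL at the on-treatment visits (Days 2/3, 6 and 8) and for viral AUC.
3. Estimate it by ANCOVA with pre-dose log10 titre and influenza type as covariates. Fit it in adults and in a pooled model with an age-group term, instead of a separate model in the small paediatric group.
4. Set values at or below the negativity cut-offs of section 2.2.2.3 (0.5 log10 TCID50/mL; 0.26 log10 vp/mL for influenza A and 0.3 for B) to the cut-off. Report how many patients lack a usable pre-dose value.
5. Leave later visits, when most patients may be negative, to the planned shedding proportions.

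The cost is a few lines of SAP text and standard code. It needs no new data.
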